### **8.8. Severity Assessment**

AEs will be reported using concise medical terminology (verbatim) as well as the grade from the CTCAE Version 4.03, <http://ctep.cancer.gov/reporting.ctc.html> listed in the Cancer Therapy Evaluation Program.

If required on the AE CRFs, the investigator will use the following definitions of severity in accordance with CTCAE Version 4.03 to describe the maximum intensity of the adverse event ([Appendix 5](#)).

GRADE	Clinical Description of Severity
0	No change from normal or reference range (This grade is not included in the Version 4.03 CTCAE document but may be used in certain circumstances.)
1	MILD adverse event
2	MODERATE adverse event
3	SEVERE adverse event
4	LIFE-THREATENING consequences; urgent intervention indicated
5	DEATH RELATED TO adverse event

Note the distinction between the severity and the seriousness of an AE. A severe event is not necessarily an SAE. For example, a headache may be severe (interferes significantly with the patient's usual function) but would not be classified as serious unless it met one of the criteria for SAEs, listed above.

### **8.9. Causality Assessment**

The investigator's assessment of causality must be provided for all AEs (serious and non-serious); the investigator must record the causal relationship in the CRF, as appropriate, and report such an assessment in accordance with the SAE reporting requirements if applicable. An investigator's causality assessment is the determination of whether there exists a reasonable possibility that the investigational product caused or contributed to an AE; generally the facts (evidence) or arguments to suggest a causal relationship should be provided. If the investigator does not know whether or not the investigational product caused the event, then the event will be handled as "related to investigational product" for reporting purposes, as defined by the sponsor (see the section on [Reporting Requirements](#)). If the investigator's causality assessment is "unknown but not related to investigational product," this should be clearly documented on study records.

In addition, if the investigator determines that an SAE is associated with study procedures, the investigator must record this causal relationship in the source documents and CRF, as appropriate, and report such an assessment in accordance with the SAE reporting requirements, if applicable.

For combination study treatment, causality assessment will be performed for each of the individual drugs in the combination.

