As of 09 June 2016, a total of 53 patients were treated in the dose escalation phase of the EMR100070-001 study, with 4, 13, 15, and 21 patients treated with avelumab doses of 1, 3, 10, and 20 mg/kg Q2W, respectively. None of the patients treated with doses up to 10 mg/kg experienced a dose limiting toxicity (DLT), and the 10 mg/kg dose of avelumab was thus considered a safe and well tolerated dose for further investigation in the dose expansion cohorts. One DLT (a Grade 3 immune related adverse event characterized by increased creatine kinase, myositis, and myocarditis) was observed in 1 patient at the dose of 20 mg/kg.

The dose expansion phase of study EMR100070-001 included patients with non-small cell lung cancer, gastric cancer, breast cancer, colorectal cancer, castration resistant prostate cancer, adrenocortical carcinoma, melanoma, mesothelioma, urothelial carcinoma, ovarian cancer, renal cell carcinoma, and squamous cell cancer of the head and neck. Study EMR100070-003 Part A was conducted in patients with Merkel cell carcinoma.

A summary of pooled safety data from patients treated at 10 mg/kg Q2W in studies EMR100070-001 and EMR100070-003 (N=1738) is provided here.

Treatment-emergent adverse events (TEAEs) were observed in 1697 (97.6%) patients, with the most frequent ( $\geq 10\%$ ) being fatigue (32.4%), nausea (25.1%), diarrhea (18.9%), constipation (18.4%), decreased appetite (18.4%), infusion related reaction (17.1%), weight decreased (16.6%), vomiting (16.2%), anemia (14.9%), abdominal pain (14.4%), cough (13.8%), pyrexia (13.6%), dyspnea (13.2%), edema peripheral (11.9%), back pain (11.8%), and arthralgia (10.4%).

Treatment-related TEAEs were observed in 1164 (67.0%) patients, and the most frequent ( $\geq 5\%$ ) were fatigue (17.7%), infusion related reaction (17.0%), nausea (8.6%), diarrhea (7.1%), chills (6.7%), pyrexia (6.1%), decreased appetite (5.2%), and hypothyroidism (5.0%).

A total of 177 patients (10.2%) experienced Grade  $\geq 3$  treatment-related TEAEs, and the most frequent ( $\geq 0.5\%$ ) were fatigue (1.0%), lipase increased (1.0%), gamma glutamyltransferase (GGT) increased (0.6%), infusion related reaction (0.6%), and aspartate aminotransferase (AST) increased (0.5%).

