#### **1.3. Summary of Benefit/Risk Assessment**

An evaluation of the anticipated benefits and risks as required in Article 3(2)(a) of Directive 2001/20/EC (cf. Article 6(3)(b) of Directive 2001/20/EC) has been conducted.

The benefit-risk relationship has been carefully considered in the planning of the trial. Avelumab has demonstrated clinical activity in patients with advanced solid tumors in an expansion cohort of an ongoing Phase 1 Trial EMR 100070-001. The clinical safety data with single-agent avelumab in patients with advanced solid tumors available to date suggest an acceptable safety profile of the compound and no differences in the overall safety profile for patients with SCCHN relative to all patients. Most of the observed events were either in line with those expected in patients with advanced solid tumors or with those observed with other antibodies blocking the PD-1/PD-L1 axis (see [Section 1.2.2.1](#)). Infusion-related reactions including hypersensitivity and irAEs/autoimmune disorders have been identified as important risks for avelumab. Respective risk mitigation measures have been implemented in all ongoing clinical studies with avelumab, including this clinical trial protocol. These include guidelines for treatment interruption and discontinuation in case of irAEs, as well as mandatory pre-treatment with a histamine H1 receptor (H1) blocker and acetaminophen. Risk mitigation measures for AEs associated with CRT are discussed in their respective sections.

As reported by Ang et al. from Study RTOG0522, among patients with previously untreated Stage III to IV squamous cell carcinoma of the oropharynx, hypopharynx, or larynx treated with combination of radiotherapy over 6 weeks, and cisplatin (100 mg/m^2 on Days 1 and 22 of radiotherapy) (N=447), Grade 3-4 treatment-related toxicities were reported in 87% of

patients. The most commonly reported Grade 3-4 non-hematological toxicities involved the gastrointestinal tract and included adverse events of dysphagia (57%), radiation mucositis (33%), mucositis/stomatitis of pharynx (24%), dehydration (15%), nausea (14%), and vomiting (9%). Skin reactions inside the portal were reported in 79% of patients (all severity grades) with 15% of patients experiencing Grade 3/4 events. The most frequently reported hematological toxicities included leukopenia (19%), neutrophil count decreased (16%), and lymphopenia (13%).

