### **9.5.1. Adverse Events**

Adverse events will be classified using the medical dictionary for regulatory activities (MedDRA) classification system. The severity of the toxicities will be graded according to the NCI CTCAE v4.03 whenever possible (<http://ctep.info.nih.gov/reporting/ctc.html>). The frequency of patients experiencing treatment emergent adverse events corresponding to body systems and MedDRA preferred term will be reported. Adverse events will be graded by worst NCI CTCAE v4.03 severity grade, and will be summarized by relatedness to study treatment.

Emphasis in the analysis will be placed on AEs classified as treatment emergent. Adverse events leading to death or discontinuation of study treatment, events classified as NCI CTCAE v4.03 Grade  $\geq 3$ , trial drug-related events, and serious adverse events will be considered with special attention. As appropriate, the difference in risk between treatment arms for AEs of clinical interest may be further assessed as described in the SAP.

Detailed information collected for each AE will include a description of the event, duration, whether the AE was serious, intensity, relationship to study treatment, action taken, and clinical outcome. Acute toxicities and late toxicities will also be summarized separately.

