### 3.4. Baseline Variables

#### 3.4.1. Study drug, study treatment and baseline definitions

In this study, ‘**study drug**’ refers to avelumab, avelumab-matching placebo, cisplatin or IMRT and ‘**study treatment**’ (or ‘**treatment arm**’) refers to one of the following:

- Arm A = Avelumab + SOC CRT;
- Arm B = Placebo + SOC CRT.

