### 6.6.1. Adverse events

Treatment-emergent adverse events (TEAEs) are those events with onset dates occurring during the on-treatment period as defined in Section 3.5.1.

All analyses described will be based on TEAEs (started during the on-treatment period) if not otherwise specified. The AE listings will include all AEs (whether treatment-emergent or not). AEs with onset outside the on-treatment period will be flagged in the listings.

- **Related Adverse Events:** adverse events with relationship to study treatment (as recorded on the AE eCRF page, Relationship with study treatment = Related) reported by the investigator and those of unknown relationship (ie, no answer to the question ‘Relationship with study treatment’). Related AEs are those related to any study drug (ie, at least one of the study drugs).
- **Serious Adverse Events (SAE):** serious adverse events (as recorded on the AE eCRF page, Serious Adverse Event = Yes).
- **Adverse Events Leading to Dose Reduction:** adverse events leading to dose reduction of study treatment (as recorded on the AE eCRF page, Action taken with study treatment = Dose reduced).
- **Adverse Events Leading to Interruption of Study Treatment:** adverse events leading to interruption of study treatment (as recorded on the AE eCRF page, Action taken with study treatment = Drug interrupted). The eCRF does not allow for a clear separation between interruption of an infusion and delays of administration for a parenteral drug as both are recorded using the same term on the eCRF (“Drug interrupted”). IRRs will be excluded in the analysis of AEs leading to Drug Interruption in case they only led to an interruption of the infusion.

- **Adverse Events Leading to Permanent Treatment Discontinuation:** adverse events leading to permanent discontinuation of study treatment (as recorded on the AE eCRF page, Action taken with study treatment = Drug withdrawn).
- **Adverse Events Leading to Death:** adverse event leading to death (as recorded on the AE eCRF page, Outcome = Fatal, as well as AEs of Grade 5).
- **Immune-related Adverse Events (irAE):** irAEs (as identified according to the methodology outlined in Appendix 1 for a pre-specified search list of MedDRA PTs documented in the SRP and finalized for analysis of this study's data prior to DB lock)

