#### 6.6.1.1. All adverse events

Adverse events will be summarized by worst severity (according to NCI-CTCAE version 4.03) per patient, using the latest version of MedDRA preferred term (PT) as event category and MedDRA primary system organ class (SOC) body term as Body System category.

In case a patient has events with missing and non-missing grades, the maximum of the non-missing grades will be displayed. No imputation of missing grades will be performed.

The following tables will be created:

- The overall summary of AEs table will include the frequency (number and percentage) of patients with each of the following by treatment arm:
  - TEAEs;
  - TEAEs, Grade  $\geq 3$ ;
  - Related TEAEs;
  - Related TEAEs, Grade  $\geq 3$ ;
  - TEAEs leading to dose reduction of avelumab;
  - TEAEs leading to dose reduction of cisplatin;
  - TEAEs leading to dose reduction of IMRT;
  - TEAEs leading to interruption of avelumab;

- TEAEs leading to interruption of cisplatin;
  - TEAEs leading to interruption of IMRT;
  - TEAEs leading to discontinuation of avelumab;
  - TEAEs leading to discontinuation of cisplatin;
  - TEAEs leading to discontinuation of IMRT;
  - TEAEs leading to discontinuation of any study drug (CRT Phase);
  - TEAEs leading to discontinuation of all study drugs (CRT Phase);
  - Related TEAEs leading to discontinuation of avelumab;
  - Related TEAEs leading to discontinuation of cisplatin;
  - Related TEAEs leading to discontinuation of IMRT;
  - Related TEAEs leading to discontinuation of any study drug (CRT Phase);
  - Related TEAEs leading to discontinuation of all study drugs (CRT Phase);
  - Serious TEAEs;
  - Related Serious TEAEs;
  - TEAEs leading to death;
  - Related TEAEs leading to death;
  - irAEs;
  - IRRs.
- TEAEs by SOC and PT and worst grade
  - Related TEAEs by SOC and PT and worst grade
  - TEAEs leading to death by SOC and PT
  - Related TEAEs leading to death by SOC and PT

In addition, the following tables will be created by treatment phase:

- Overall summary of AEs table will include the frequency (number and percentage) of patients with each of the following by treatment arm and treatment phase a :
  - TEAEs;
  - TEAEs, Grade  $\geq$  3;
  - TEAEs leading to discontinuation of avelumab;
  - Serious TEAEs;
  - irAEs;
  - IRRs.
- TEAEs by SOC and PT and worst grade.

- TEAEs leading to death by SOC and PT.

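### An adverse event counts as related if any study drug is implicated, so the overall related rows say little about avelumab, although the protocol asks for causality drug by drug

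*Protocol*

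**What the plan says.** Protocol 8.9 sets the collection rule: "For combination study treatment, causality assessment will be performed for each of the individual drugs in the combination". Protocol 9.5.1 sets the analysis at a coarser level: events "will be summarized by relatedness to study treatment".

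SAP 6.6.1 fixes the definition used in the tables: "Related AEs are those related to any study drug (ie, at least one of the study drugs"). It adds "those of unknown relationship (ie, no answer to the question ‘Relationship with study treatment"), so an unanswered question also counts as related. SAP 3.4.1 makes the net wide, because study drug "refers to avelumab, avelumab-matching placebo, cisplatin or IMRT and" is defined separately from treatment arm. An event put down to radiotherapy alone is therefore a related event.

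SAP 6.6.1.1, 6.6.1.4 and 6.6.3 use this single definition for related events overall, at Grade 3 or higher, serious, fatal, and leading to discontinuation. One of these tables is "Related TEAEs by SOC and PT and worst grade". The discontinuation tables are split by the drug that was stopped, but not by the drug blamed. The by-phase tables contain no related row.

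**The concern.** Both arms receive cisplatin and radiotherapy, and most patients have severe toxicity from them. Under an any-drug rule, a patient with a CRT-related Grade 3 event is already counted. A further event attributed to avelumab does not change that patient's status in the overall row. The row is pushed towards its ceiling in both arms and can be read as showing similar related toxicity with and without avelumab.

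The discontinuation table has a different fault. An event attributed only to cisplatin or IMRT, after which avelumab was stopped, enters the related table for avelumab discontinuation. The table's title does not tell the reader this.

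The protocol's own benchmarks for single-agent avelumab (section 1.2.2) are rates of events related to avelumab: 10.2% Grade 3 or higher, 6.2% serious and 6.2% leading to discontinuation. No planned related table can be set beside them.

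**Working it through.** No sample size, power or alpha in the plan depends on this definition, so there is no planned figure to reproduce. The check is an illustration of how visible an avelumab effect would be.

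**Inputs**
- CRT background b. Protocol 1.3, on a trial with 6-week radiotherapy and two cisplatin doses: "Grade 3-4 treatment-related toxicities were reported in 87% of" patients. A second trial in the same section, with 70 Gy in 35 fractions and three cisplatin cycles, gives about 80% with Grade 3 to 5 toxicity; the protocol does not label that figure treatment-related.
- Avelumab-related Grade 3 or higher, a. Protocol 1.2.2: "A total of 177 patients (10.2%) experienced Grade" 3 or higher treatment-related events, and 177/1738 = 10.2%. The SCCHN cohort in 1.2.2.1 gives 3/93 = 3.2%.
- 640 patients randomized 1:1, so 320 per arm.

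**Any-drug row, Grade 3 or higher.** Assuming independence, the Arm A rate is 1 − (1 − b)(1 − a) and the Arm B rate is b. The difference is (1 − b) × a.

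| b | a | Arm A | Arm B | Difference (points) |
|---|---|---|---|---|
| 80% | 3.2% | 80.6% | 80.0% | 0.6 |
| 80% | 10.2% | 82.0% | 80.0% | 2.0 |
| 87% | 3.2% | 87.4% | 87.0% | 0.4 |
| 87% | 10.2% | 88.3% | 87.0% | 1.3 |

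A two-sided 5% comparison with 320 per arm would have power of 0.04 to 0.10 across these rows. The SAP plans no such test; power only measures visibility here.

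**Row restricted to avelumab/placebo.** Blinded investigators will attribute some events to the infusion in either arm. The documents give no rate for this, so m is assumed to be 1% to 10% in both arms. The formula is the same, with m in place of b.

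| m | a | Arm A | Arm B | Difference (points) | Power |
|---|---|---|---|---|---|
| 1% | 3.2% | 4.2% | 1.0% | 3.2 | 0.72 |
| 10% | 3.2% | 12.9% | 10.0% | 2.9 | 0.21 |
| 1% | 10.2% | 11.1% | 1.0% | 10.1 | >0.99 |
| 10% | 10.2% | 19.2% | 10.0% | 9.2 | 0.91 |

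**Preferred-term rows of the any-drug tables.** Avelumab rates are from protocol 1.2.2; CRT backgrounds are assumed.
- Infusion related reaction, 17.0%, on a 1% to 5% background: power about 1.0.
- Hypothyroidism, 5.0%, on a 1% to 2% background: power 0.93 to 0.85.
- Nausea, 8.6%, on a 30% to 60% background: power 0.37 to 0.14.

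Terms that are rare under CRT remain visible; terms that overlap with CRT are masked.

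**The case against.** The secondary objective is the overall safety of avelumab plus CRT and of CRT alone. That is a question about regimens, which randomized all-cause comparison answers without attribution. Protocol 9.5.1 itself speaks of study treatment, so the SAP definition does not contradict the protocol's analysis section. Protocol 5.5.1.3 accepts that toxicities may overlap and that the cause may rest on investigator judgment, so per-drug attribution is imperfect evidence. These points stand. They are reasons to keep the any-drug and all-cause tables, but not to leave out the drug-specific ones.

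A reader might infer that the planned tables cannot show avelumab toxicity. The documents do not support that. Related events are tabulated by blinded randomized arm down to preferred term. SAP 6.6.4 plans irAE tables, infusion reactions separated by associated drug, and risk differences with confidence intervals for irAEs, avelumab infusion reactions and Tier-2 events. All-cause events are also shown by phase, including the Maintenance Phase, when only avelumab/placebo is given. These outputs are not full substitutes: irAEs and infusion reactions must meet narrow case definitions (SAP Appendices 1 and 2), and Tier-2 contrasts for overlapping terms face the same masking.

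A reader might also infer that every related row is near its ceiling. The 80% to 87% figures concern Grade 3 or higher only. The documents give no CRT rate for any-grade, serious or fatal related events, or for related discontinuations.

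Finally, a reader might set 10.2% against a small placebo attribution and expect a large, certain gain. That ignores the SCCHN cohort's 3.2%, and false attribution must be allowed in both arms.

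**Conclusion.** The gap is real but limited. The protocol asks for causality per drug; the SAP collapses it to any drug, and no planned table shows events attributed to avelumab/placebo. The loss is confined to the overall related rows and to terms that overlap with CRT. The discontinuation tables have the added problem that the drug stopped and the drug blamed need not match.

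For the related Grade 3 or higher row, avelumab shifts the any-drug rate by about 0.4 to 2.0 points. A restricted row would shift by about 3 points at the SCCHN cohort rate, or 9 to 10 points at the pooled rate. These figures assume independence, the protocol's CRT background (partly from a different regimen), and 1% to 10% attribution to placebo in both arms. At 3.2% the gain is modest and the contrast may still be unclear.

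Efficacy analyses and type I error are unaffected. This is a low-cost improvement to safety reporting.

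**What to change.** First confirm that the AE eCRF stores relationship separately for avelumab/placebo, cisplatin and IMRT. SAP 6.6.1 names only one relationship field, and protocol 8.9 refers to drugs, which leaves IMRT unclear. If relationship is not stored per drug, protocol 8.9 is not being carried out and that needs its own correction.

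If it is, then in SAP 6.6.1:
- Define events related to avelumab/placebo from the per-drug entry, and state how a missing entry for that drug is handled.
- Add tables on that definition for related events overall, at Grade 3 or higher, serious, and leading to death, by arm and by SOC and preferred term.
- For related events leading to discontinuation of a given drug, require relatedness to that same drug.
- Keep the any-drug tables, labelled as such.

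A by-phase version of the restricted tables would be a useful option, since no related table is now produced by phase.

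If the per-drug entries exist, the cost is SAP wording and a few more tables from data collected under the blind, with no new work for sites. The drawback is that the new tables depend on investigators' attribution of overlapping toxicities, which a footnote should say.

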## 8.10. Exposure During Pregnancy

For both unapproved/unlicensed products and for marketed products, an exposure during pregnancy occurs if:

1. A female becomes, or is found to be, pregnant either while receiving or having been exposed (eg, because of treatment or environmental exposure) to the investigational product; or the female becomes or is found to be pregnant after discontinuing and/or being exposed to the investigational product;

An example of environmental exposure would be a case involving direct contact with a Pfizer product in a pregnant woman (eg, a nurse reports that she is pregnant and has been exposed to chemotherapeutic products).

2. A male has been exposed (eg, because of treatment or environmental exposure) to the investigational product prior to or around the time of conception and/or is exposed during his partner's pregnancy.

If a study patient or study patient's partner becomes or is found to be pregnant during the study patient's treatment with the investigational product, the investigator must submit this information to the Pfizer drug safety unit on an SAE report form and an EDP supplemental form, regardless of whether an SAE has occurred. In addition, the investigator must submit information regarding environmental exposure to a Pfizer product in a pregnant woman (eg, a patient reports that she is pregnant and has been exposed to a cytotoxic product by inhalation or spillage) using the EDP supplemental form. This must be done irrespective of whether an AE has occurred and within 24 hours of awareness of the exposure. The information submitted should include the anticipated date of delivery (see below for information related to termination of pregnancy).

Follow-up is conducted to obtain general information on the pregnancy and its outcome for all EDP reports with an unknown outcome. The investigator will follow the pregnancy until completion (or until pregnancy termination) and notify Pfizer of the outcome as a follow-up to the initial EDP supplemental form. In the case of a live birth, the structural integrity of the neonate can be assessed at the time of birth. In the event of a termination, the reason(s) for termination should be specified and, if clinically possible, the structural integrity of the terminated fetus should be assessed by gross visual inspection (unless preprocedure test findings are conclusive for a congenital anomaly and the findings are reported).

If the outcome of the pregnancy meets the criteria for an SAE (ie, ectopic pregnancy, spontaneous abortion, intrauterine fetal demise, neonatal death, or congenital anomaly [in a live-born baby, a terminated fetus, an intrauterine fetal demise, or a neonatal death]), the investigator should follow the procedures for reporting SAEs.

Additional information about pregnancy outcomes that are reported as SAEs follows:

- Spontaneous abortion includes miscarriage and missed abortion;
- Neonatal deaths that occur within 1 month of birth should be reported, without regard to causality, as SAEs. In addition, infant deaths after 1 month should be reported as SAEs when the investigator assesses the infant death as related or possibly related to exposure to the investigational product.

Additional information regarding the EDP may be requested by the investigator. Further follow-up of birth outcomes will be handled on a case-by-case basis (eg, follow-up on preterm infants to identify developmental delays). In the case of paternal exposure, the investigator will provide the study patient with the Pregnant Partner Release of Information Form to deliver to his partner. The investigator must document in the source documents that the patient was given the Pregnant Partner Release of Information Form to provide to his partner.

